### Familiarisation day

# 09:00 Check inclusion/ exclusion criteria Consent Complete all demographic info 09:45 Complete first assisted cognitive/mood battery 10:45 Short break if needed [experimenter to check data] 11:15 Second run through of battery 12:15 Confirm happy to continue Send home with sample kit and instructions

Using 23 hours (rather than 24) allows us to keep in line with the time at which cognitive baseline measures were recorded. We see significant time of day effects on cognition, so keeping the times consistent within participants at all test points is important to allow more reliable and sensitive assessment of intervention effects

### **Baseline**

08:30   09:15	

Collect faecal sample

Standardised breakfast

09:00   09:45 10:00   10:45	

Cognitive/mood battery

Administer intervention

All other test days (23 hours, 4 and 8 weeks)

Standardised breakfast

09:00 | 09:45 Cognitive/mood battery

# Justification for chosen outcome measures

Outcome measure	Supporting evidence
An emotional recognition/decision task (TBC)	Significant positive effect on both emotional recognition and decision tasks following probiotic intervention compared with placebo  (both used Winclove multi-strain products)
	Findings also supported by fMRI data suggesting altered affective processing following supplementation with a fermented milk product 
Ray Auditory Verbal Learning Task	Some evidence to support positive effect on verbal memory using AVLTs in a depressed population  , volunteers with HIV-1  (although a few flaws in this study) and healthy adults  (although open-label).
	There is an overlap here of probiotics used in each study, including Lactobacillus plantarum , Bifidobacterium breve and Bifidobacterium longum .
Corsi blocks	Studies have found protective effect of probiotics on WM under stress  . Unclear whether an effect without the acute stressor?
Switching task (from current battery)	A couple of studies used the switching task from CANTAB on children but found no effect, while another reported improved performance in both active and placebo groups in healthy adults  , probably due to practice effects. One other study suggests a large effect size  but is open-label and also likely to practice effects. So unclear from current literature but given potential improvements in attention could be an interesting one to include, as we know this switching task is, to a degree, an endurance test and is sensitive to nutritional interventions.
Leiden Index of Depression Sensitivity revised (LEIDS-r)	Has been used previously in studies supplementing with Ecologic barrier in healthy young adults  and patients with MDD  , where chronic supplementation was associated with a significant reduction in reactivity to sad mood. Would therefore be good to see if these findings persist in an acute trial.
Centre for Epidemiological Studies Depression Scale (CESD)	Well validated measure of depressive symptoms.
Positive and Negative Affect Schedule expanded (PANAS-x)	As there is little evidence regarding how Ecologic barrier may influence general mood, particularly in an acute setup, the PANAS-x

	would allow us to cover 11 affective states (as opposed to the POMS which is longer and covers fewer affective states)
State items from State Trait Anxiety Inventory	Good to include an anxiety measure - chronic supplementation studies have reported reductions in anxiety  . Beck Anxiety Inventory and General Anxiety Disorder-7 wouldn't work for an acute study as they ask about feelings over the last 2 weeks/month. State items from the STAI therefore work better as they ask about how you feel in that moment.

Generally, these cognitive domains have been chosen as there is evidence from more than one paper using the same or similar tasks for a positive effect of probiotic supplementation on performance. Where possible, have also tried to use tasks that have been associated with improvement following Ecologic barrier or multi-strain interventions containing similar genera.

### Sample size power calculation

Previous parallel RCTs looking at the effect of Ecologic Barrier on cognitive or mood outcomes have used between 20 and 36 subjects per group. There are some acute prebiotic studies looking at mood/cognitive outcomes – a positive effect of an intervention was reported using 30 participants in a cross-over RCT and 23 in a parallel groups RCT.

Previously, effect sizes between 0.4 and 0.6 have been reported for probiotic intervention on tasks of attention and executive function.

G\*Power calculation based on a medium effect size of 0.5:

t tests-Means: Difference between two dependent means (matched
pairs)

```
Analysis:
             A priori: Compute required sample size
Input:
             Tail(s)
                                                    One
             Effect size dz
                                                    0.5
                                                    0.05
             α err prob
             Power (1-\beta \text{ err prob})
                                                    0.8
Output:
             Noncentrality parameter \delta
                                                    2.5980762
                                                =
             Critical t
                                                    1.7056179
                                                    26
             Df
             Total sample size
                                                    27
                 Actual power
     0.8118316
```

Based on this information, we should aim for a sample of N=30.

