#### **Design**

Double-blind, cross-over, randomised control trial. All outcomes measured at baseline, 23 hours, 4 weeks and 8 weeks (*see page 3 for explanation*).

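### Does sizing this cross-over on a matched-pairs t test leave the practice effect in the error term and the trial short of power?

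*Protocol*

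**What the plan says.** The Design section calls the trial a "Double-blind, cross-over, randomised control trial". The schematic gives each participant two arms, each with its own T0 battery followed by an acute, a week-4 and a week-8 battery.

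Under Sample size power calculation, the protocol shows G*Power output for "t tests-Means: Difference between two dependent means". The inputs are a one-sided test at 0.05, target power 0.8, and a "calculation based on a medium effect size of 0.5". The output is 27 participants, 26 degrees of freedom and actual power 0.8118316. The section ends by saying "we should aim for a sample of N=30".

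On practice, the Switching task row of the outcome justification table reports that one cited study found "improved performance in both active and placebo groups in healthy adults", "probably due to practice effects". The protocol also takes steps against practice: the Cognitive Outcomes section requires parallel test versions, and the Familiarisation day includes at least two practice runs of the battery.

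The protocol has no section on the analysis of outcomes. It does not say which model will be fitted, whether period is included, or whether raw scores or changes from each arm's T0 are to be compared.

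**The concern.** In a two-period cross-over, a general shift from arm 1 to arm 2 enters the active-minus-placebo difference with opposite signs in the two sequences. It adds for those who take active second and subtracts for those who take it first. A plain matched-pairs t test has no term for this and treats the spread between sequences as random error. The 26 degrees of freedom for 27 people confirm that no period term was in the calculation, since a period-adjusted comparison would have 25.

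Participants take the battery at least ten times (two practice runs and eight test sessions), and the protocol names practice as a likely explanation of one earlier result. If the outcomes were analysed by the plain paired test and a sizeable shift remained, power would be lost without need. If dropout left the sequences unequal, part of the shift would also bias the estimate.

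**Working it through.** **Inputs from the protocol.** One-sided alpha 0.05, dz = 0.5, computed n = 27, planned N = 30.

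**Assumed input.** P is the arm-2 minus arm-1 shift in SDs of the paired difference. The documents give no value, so a range of 0 to 1.0 is used.

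**Step 1: the protocol's figure.** The noncentrality is dz × √n = 0.5 × √27 = 2.598. With 26 df the one-sided critical value is 1.7056. Noncentral t power is 0.8118, which matches the output. At N = 30 the noncentrality is 0.5 × √30 = 2.739 and power is 0.8483.

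**Step 2: the same effect under a period-adjusted cross-over test.** The treatment estimate is the average of the two sequence means of the within-person difference. Its standard error is √[(1/n₁ + 1/n₂)/4], with n − 2 df and unit SD within sequence.
- n = 27 split 13/14: SE = √[(1/13 + 1/14)/4] = 0.1926; noncentrality 0.5/0.1926 = 2.596; 25 df; power 0.8106.
- N = 30 split 15/15: SE = √[(1/15 + 1/15)/4] = 0.1826; noncentrality 2.739; 28 df; power 0.8477.

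These powers do not depend on P. Moving from the paired test to the period-adjusted test costs 0.8118 − 0.8106 = 0.0012 at n = 27 and 0.8483 − 0.8477 = 0.0006 at N = 30. The 27 participants still exceed 80%, provided dz is read as the effect over the SD of the difference net of period.

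**Step 3: what the plain paired test would lose if it were used.** The within-person difference is 0.5 + P in one sequence and 0.5 − P in the other, with unit SD. Simulated one-sided power (400,000 trials per case; the n = 27 column averages the 13/14 and 14/13 splits):

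| P | Paired, n = 27 | Paired, N = 30 (15/15) |
|---|---|---|
| 0 | 81% | 85% |
| 0.25 | 80% | 83% |
| 0.5 | 75% | 79.5% |
| 0.75 | 67% | 73% |
| 1.0 | 57% | 63% |

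At the planned 30, a shift as large as the assumed treatment effect leaves 79.5% with equal sequences, or 77.2% if each participant is allocated by simple randomisation. Power falls well below target only for larger shifts; P = 1.0 is twice the assumed treatment effect. With equal sequences the paired estimate is unbiased and the test is conservative: at N = 30 and P = 0.5 its type I error is 3.3%.

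**Step 4: what the document commits to.** The losses in Step 3 require the plain paired test on raw scores to be the analysis. The Sample size section does not say what is paired. Both arms have a T0 battery before dosing, so the pair could equally be two changes from baseline. A shift that raises all of arm 2 by a constant then cancels: (Y + P) − (T0 + P) = Y − T0.

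**The case for a change.** The strongest reply is that the complaint concerns what the protocol states, not what it omits. It declares a cross-over, yet the one test it names is a test without period. Practice runs and parallel versions reduce learning but are not shown to remove it. If learning is steeper in arm 1 than in arm 2, even change scores carry a period effect. And with two eight-week arms, losses from 30 are likely; with sequences of 17 and 13 and P = 0.5, the paired estimate would move by 0.5 × (17 − 13)/30 = 0.067, from 0.50 to 0.43 or 0.57.

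Each of these statements is correct given its premises. They show that a period term is good practice here, and that the powers in the table would apply if it were left out. They do not show that it has been left out. A simple paired calculation is a common way to size a cross-over, and it does not bind the analysis. If the SAP fits period, the stated power is right to within about 0.001. The remark about practice concerns one cited study of one task, in which both groups improved; it gives no size for a shift between arms after training on parallel forms. The 17/13 split and every value of P are assumptions.

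**Conclusion.** No fault in the protocol is shown. The paired t test is a sizing device and not the adopted analysis. Replacing it with the usual period-adjusted comparison changes power by about 0.001 (0.8118 to 0.8106 at 27; 0.8483 to 0.8477 at 30), so neither the computed 27 nor the planned 30 would change.

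The apparent drop from 81% to 75% depends on three things the protocol does not say: that the plain paired test will be the analysis, that raw scores will be paired, and that the shift is 0.5 SD. It is also worked at 27 participants, while the plan is 30, where the same shift gives 79.5% in equal sequences.

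This conclusion rests on dz being net of period and on the SAP, which is not shown, being the place where the period, sequence and baseline terms are fixed. It covers the period effect only; it does not judge the one-sided test, the choice of 0.5, or the allowance for dropout.
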